1.20 Multicenter management and coordination

1.20.1 Data Management

1.20.1.1 Data Submission

Data will be collected and managed in Yale's web-based clinical trial management system, OnCore. The schedule for completion and submission of the electronic case report forms will be indicated within OnCore. The investigators are required to prepare and maintain adequate and accurate case histories designed to record all observations and other data pertinent to the investigation on each individual treated in the investigation. Data that are derived from source documents and reported on the eCRF must be consistent with the source documents or the discrepancies must be explained.

1.20.1.2 Monitoring

The study principal investigator and YCCI are responsible for monitoring the performance of all of the participating sites. This will be performed by conducting a study site initiation visit, as well as regularly scheduled monitoring visits and/or remote monitoring throughout the life of the protocol. At the end of the trial, the monitor will then perform a study site close-out visit at all participating sites.

YCCI will utilize their institution's initiation, monitoring and close-out visit reports. Following each site visit, a visit report will be generated containing information on site activities, and a summary of pertinent points and action items together with a copy of the follow-up letter will be sent to each investigative site.

During these monitoring visits, some of the items that will be reviewed are the following:

- Training of the sites
- Site personnel qualifications to participate in the trial
- Confirmation that study related documents are current
- Regulatory documents and compliance
- Completion of informed consent by each subject
- Compliance with the protocol
- Confirm all SAEs and AEs have been reported to the local regulatory and Ethics/IRB Committees, BI and YCCI, as appropriate
- Verify source documentation for completed CRFs
- YCCI will document the required study monitoring activities in a Monitoring Plan.

1.20.2 Safety Evaluations

Safety analysis will be conducted on all participants who have received at least one dose of therapy, and will include the frequency of all AEs and laboratory abnormalities as well as frequency of dose interruptions, dose reductions, and treatment discontinuation. Participants who receive one total cycle of treatment will be considered as having completed the evaluation for safety. Additional treatment cycles may be delivered if there are no safety concerns, there is no disease progression, and/or there is an indication of clinical benefit. Maintenance monitoring will occur on day 1 of every additional treatment cycle, unless indicated.

Any safety concern or new information that might affect either the safety or the ethical conduct of this trial will be immediately forwarded to the principal investigator in written form. The principal investigator will be responsible for informing the IRB and Data and Safety Monitoring Committee (DSMC). If trends in toxicities are noted or stopping rules are met, the principal investigator will temporarily suspend enrollment while reviewing the episodes with the IRB and DSMC. Toxicity data must be submitted via OnCore at the end of each cycle of therapy.

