1.6 Definition of dose limiting toxicities (DLT) during phase I

In order to determine safety of the combination, all adverse events will be recorded on the case report forms and graded using the NCI CTC criteria (version 4.03). Toxicities not listed on the CTC will be graded as mild, moderate, or severe. The local Investigator, in consultation with the clinical staff caring for the patient, and the Protocol PI will determine the relationship to study drugs (unrelated, unlikely, possibly related, probably related, related). Dose limiting toxicity (DLT) will be either as specified below; for organ systems not included, DLT will also include any Grade III or IV non-hematologic toxicity thought possibly or probably related to study drug administration.

Specifically defined DLTs: Drug-related vomiting and nausea CTCAE grade \geq 2 for 5 or more consecutive days despite optimal supportive care. Drug-related diarrhea CTCAE grade \geq 2 persisting for 8 or more consecutive days despite optimal supportive care. Drug-related hypertension CTCAE grade \geq 3 despite optimal supportive care or intervention.

Drug-related transaminase elevation (ALT and/or AST) CTCAE grade \geq 3 or transaminase elevation CTCAE grade \geq 2 (ALT and/or AST) in conjunction with bilirubin CTCAE grade >1 . All other drug-related non-hematological toxicities of CTCAE grade \geq 3, except for isolated GGT increases. All other drug-related non-hematological toxicities of CTCAE grade 2 leading to an interruption of the BIBF 1120 treatment for \geq 14 consecutive days

Because all patients will be receiving cytarabine and idarubicin in conjunction with nintedanib, patients will not be evaluable for nintedanib- associated hematological toxicity.

Patients will have bone marrow assessed at physician's discretion by day 35 of treatment. If blood counts have not recovered, but marrow is free of morphologic evidence of leukemia, patients may be followed clinically until day 45. If counts have not recovered by day 60 and there is no morphologic evidence of leukemia, this will be considered a nintedanib- associated hematologic DLT.

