If <2/6 patients experience Nintedanib attributable dose limiting toxicity, we will proceed to the randomized Phase II trial. If >/= 2 patients experience attributable DLT, six additional patients will be treated with dose level - 1 of nintedanib (150 mg BID). Assuming that <2/6 patients experience Nintedanib attributable dose limiting toxicity at the reduced dose, we will proceed to the randomized Phase II trial -1 dose level of nintedanib.

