1.7 Statistical plan

The feasibility phase is structured similar to a classic 3 + 3 Phase I study. The first six patients will be treated at the targeted dose. Like most Phase I studies, this dose will be considered feasible if <2/6 patients experience attributable DLT. If at least two patients experience attributable DLT, six additional patients will be treated at dose level -1. If fewer than 2 patients experience attributable DLT, that dose will be used in the Randomized Phase II portion of the trial.

The primary endpoint of the Randomized Phase II portion is the complete remission rate. The randomized phase II portion of the study utilizes a group sequential design to test the hypothesis that arm A (nintedanib+chemotherapy) will have a complete response rate of 40% after one cycle of treatment compared to 15% in arm B (Placebo+chemotherapy). Estey, Thall, and David reviewed the outcomes of salvage therapy for AML⁴⁸. They stratified patients based on length of first remission (S1: if greater than 2 years) and whether the therapy was first or subsequent salvage (S2: first remission 1 – 2 years, S3: First remission 0- 1 year, first salvage: S4: First remission 0 – 1 year, receiving > first salvage). CR rates for S2, 3, and 4 were 47%, 14%, and 0. We will not be treating S1 in this protocol. Thus, a 40% response rate appears to be very robust for a mix of S2 to S4 patients. While it is highly unlikely that the control (placebo) arm will have a comparable CR rate, without the control arm the success of the addition of nintedanib will not be clear. Using the group sequential design we will minimize the number of patients receiving placebo. For example, if 0/8 patients in the placebo arm achieve remission, the arm will be stopped for futility. In contrast, if 5/11 patients in the nintedanib arm achieve CR, the study can be declared a success.

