For Phase II, OnCore will be used to randomize the patients by assigning a sequence number that will correspond to the treatment assignment. The list that includes the sequence number with the corresponding treatment assignment will be generated by the study statistician and released only to the research pharmacist at the site. The group sequential design allows termination of either arm at early time points due to either futility or efficacy. In a randomized Phase II trial, each arm is compared to a historic control. The studies are not powered to officially compare the arms. Rather, they serve as “pick the winner” strategies. The null hypothesis is that each arm achieves a 15% response rate. The trial is powered to select an arm (presumably the experimental arm) which achieves a 40% response rate. At the point at which either arm can no longer demonstrate a 40% response rate, the arm is terminated for futility. Each arm is monitored following each accrual beginning with patient 8. The design assumes overall Type I error of 10% (1-sided) and 80% power.

The following table demonstrates the number of responses at each accrual which would stop the trial for either futility (third column) or efficacy (fourth column):

Analysis	Number of included patients	Number of responses to stop for futility	Number of responses to stop for efficacy
1	8	0	4
2	9	1	4
3	10	1	5
4	11	1	5
5	12	2	5
6	13	2	5
7	14	2	6
8	15	2	6
9	16	3	6
10	17	3	7
11	18	3	7
12	19	3	7
13	20	4	7
14	21	4	8
15	22	4	8
16	23	4	8
17	24	5	8

While this is a randomized Phase II study and each arm is ultimately statistically compared to the historical control, the response rates will be qualitatively compared between the two arms in order to get a sense whether the positive signal in the nintedanib arm is strong enough to warrant further development in larger trials.

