1.20.3 Safety Monitoring

1.20.3.1 Data and Safety Monitoring Committee

The Yale Cancer Center Data and Safety Monitoring Committee (DSMC) will provide the primary oversight of data and safety monitoring. The Yale DSMC will review and monitor compliance, toxicity and deviations from this study. The committee is composed of clinical specialists with experience in oncology and who have no direct relationship with the study. Information that raises any questions about participant safety will be addressed with the Principal Investigator.

The DSMC will review this protocol bi-annually, at a minimum. Information to be provided to the committee includes: a study narrative by the PI, a summary DSMC report produced by OnCore (which includes participant accrual, response, trial status history, SAEs, Adverse Events, Deviations and survival); audit results, and monitoring reports as applicable. Other information (e.g. scans, laboratory values) will be provided upon request.

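### Section 1.20.2 pauses enrolment when stopping rules are met, but the protocol states no count-based toxicity stopping rule for Phase II

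*Combined protocol and SAP*

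**What the plan says.** Section 1.20.2 gives two grounds for pausing accrual: "If trends in toxicities are noted or stopping rules are met, the principal investigator will temporarily suspend enrollment". It neither states the stopping rules nor says where they are.

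The other provisions that bear on toxicity are these:

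- **Phase I.** Section 1.6 is headed "Definition of dose limiting toxicities (DLT) during phase I". Under section 1.7, "The first six patients will be treated at the targeted dose" and "this dose will be considered feasible if <2/6 patients experience attributable DLT". Otherwise, "If at least two patients experience attributable DLT, six additional patients will be treated at dose level -1".
- **Phase II boundaries.** Section 1.7: "Each arm is monitored following each accrual beginning with patient 8". The table runs from 8 to 24 patients per arm, and its futility and efficacy columns both count responses.
- **Termination.** Section 1.17 lets the sponsor suspend or end the trial for unexpectedly frequent or severe toxicity, with no threshold.
- **Committees.** Section 1.20.3.1: "The DSMC will review this protocol bi-annually, at a minimum". Section 1.20.3.2 guarantees one safety review committee meeting, after the first six patients; further meetings are at the sponsor's request.
- **Patient-level rules.** Section 1.5.2 has numeric thresholds for interrupting or reducing nintedanib or placebo. They govern one patient's drug, not enrolment.
- **Allocation.** Under section 1.7 the study statistician generates the list, and only the site research pharmacist receives it.

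**The concern.** A clause that makes suspension mandatory when a rule is met needs a rule. In Phase II there is none to meet, so that half of the clause cannot operate and only the judgement of a trend remains.

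That judgement falls to a principal investigator who does not hold the allocation list, in a blinded comparison where both arms receive intensive chemotherapy. Section 1.20.3.1 does not say that the DSMC's report is split by arm. An excess on nintedanib could be diluted in pooled data.

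The dose carried forward always rests on six patients, because a failed first dose leads to six new patients at the lower level. Phase II then assigns 8 to 24 patients to nintedanib and offers it to placebo non-responders. Comparative safety is a stated Phase II objective in section 1.3.2, but no decision depends on it.

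**Working it through.** **1. The plan's own sample size.** Section 1.1 gives 22 to 60 patients. Minimum: 6 + 2 × 8 = 22. Maximum: 12 + 2 × 24 = 60. Both reproduce. After the six-patient gate, up to 24 patients are assigned to nintedanib and up to 24 more could cross over, so up to 24 + 24 = 48 could be exposed.

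**2. What the gate can exclude.** The documents give no unacceptable DLT rate, so the true rate p is an assumption shown over a range. The gate passes with 0 or 1 DLT in 6:

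P(pass) = (1 − p)^6 + 6p(1 − p)^5

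| True DLT rate | 0 of 6 | 1 of 6 | P(pass) |
|---|---|---|---|
| 20% | 0.262 | 0.393 | 0.655 |
| 33% | 0.090 | 0.267 | 0.358 |
| 40% | 0.047 | 0.187 | 0.233 |
| 50% | 0.016 | 0.094 | 0.109 |

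For a dose that passes, the upper limit of the exact two-sided 95% interval is 45.9% after 0 of 6 and 64.1% after 1 of 6.

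**3. What a boundary could add (illustration only).** Take a Beta(0.66, 1.34) prior, with mean 0.33. Pause at the smallest DLT count x among n patients for which P(rate > 33%) exceeds 0.90 under Beta(0.66 + x, 1.34 + n − x), for n = 3 to 24. This gives 3 in 4, 4 in 6, 5 in 8, 6 in 11, 7 in 13, 8 in 16, 9 in 18, 10 in 21, 11 in 23 and 12 in 24.

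If the arm always ran to 24, the pause probabilities would be 0.045, 0.266, 0.792 and 0.957 at DLT rates of 20%, 33%, 50% and 60%. Mean exposure at 50% would be 12.0.

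The arm does not always run to 24, because section 1.7 stops it on responses from patient 8. Exact recursion over that table gives a mean arm size of 11.3, 13.2 and 11.5 at response rates of 15%, 25% and 40%. Running both boundaries together over those response rates gives:

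| True DLT rate | P(pause), arm always 24 | P(pause), response table running |
|---|---|---|
| 20% | 4.5% | about 4% |
| 33% | 26.6% | 18–20% |
| 50% | 79.2% | 54–59% |
| 60% | 95.7% | 75–79% |

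Mean nintedanib-arm exposure at a 50% DLT rate falls from about 11–13 to about 8. The calculation assumes that toxicity is independent of response, that each DLT is known before the next accrual, and that the toxicity boundary is read first when one patient crosses both. Reading the response boundary first lowers the pause probabilities by a few points.

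**The case against.** The strongest reply is that Phase II is not unmonitored. The same sentence makes a toxicity trend sufficient on its own, and suspension is then mandatory. Section 1.19.6 requires SAEs and events of special interest to be reported within 24 hours. Section 1.20.2 requires safety concerns to be forwarded at once and toxicity data to be entered after each cycle. Section 1.20.5 has monthly team meetings that cover participant safety. Section 1.16 holds study drug while unblinding for an unexpected serious event is decided. Twice a year is only the DSMC's minimum. Section 1.14.1 cites 200 mg bid as the recommended dose with several other chemotherapies, though not with this regimen. The phrase about stopping rules could also mean the Phase I gate, since 1.20.2 covers the whole trial.

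Most of this stands. A reader might infer that Phase II has no safety trigger or that enrolment could never be suspended; the documents do not support that. What remains is narrower: none of these safeguards has a number, and nothing extends the Phase I gate to Phase II. The blind is also partial, because non-responders are unblinded after cycle 1, but this happens patient by patient and gives no tally by arm.

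Three other strong readings fail:

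- **Halved exposure.** A reader might infer that a boundary halves exposure from 24 to 12. That ignores the response table, which already holds the mean to 11–13.
- **Tolerance of 2 in 6.** A reader might take 2 in 6 as the plan's tolerated rate. Two DLTs in six fail the dose, so the illustrative boundary (4 in 6) is much laxer than the Phase I rule.
- **Very toxic doses.** A reader might infer that a very toxic dose is likely to reach Phase II. The gate passes a 50% rate only 11% of the time, and at 33% the illustrative boundary would pause fewer than one trial in five.

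**Conclusion.** The point holds as a gap in an operative clause: 1.20.2 relies on stopping rules that, for Phase II toxicity, the protocol does not contain. This follows from the text and needs no assumption.

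Its practical size is moderate. The six-patient gate leaves a 36%, 23% or 11% chance of carrying forward a dose with a true DLT rate of 33%, 40% or 50%. A boundary like the one illustrated would then save about 3 to 5 nintedanib-arm patients on average at a 50% rate (11.3 or 13.2 down to about 8), with a needless pause in about 4% of trials at 20%. Those benefit figures depend on the assumed 33% reference rate, the 0.90 cut-off and the independence of toxicity and response. They leave out crossover exposures. The change is worth making because a rule is already presumed and the data are already collected.

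**What to change.** 1. Apply the section 1.6 DLT definition to cycle 1 of Phase II patients assigned to nintedanib.
2. Have the study statistician, who generates the allocation list, tally DLTs by arm for the DSMC alongside the per-accrual response monitoring. Amend section 1.7 to permit this, and keep the tally from the investigators.
3. State in 1.20.2 a count boundary that pauses enrolment for DSMC review. The sponsor should set the unacceptable DLT rate, reconcile it with the Phase I rule under which 2 in 6 fails the dose, and say whether the six Phase I patients at that dose count. The boundary in the working shows the form and is not a recommended threshold.
4. Tally first nintedanib cycles after crossover separately, or extend the boundary beyond 24.

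The cost is one table and a few sentences, using the existing DSMC and the toxicity data already entered in OnCore each cycle. The drawbacks are a small chance of a needless pause, an unblinded tally that must be firewalled, and some lag, because the hematologic DLT in section 1.6 is not settled until day 60.

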1.20.3 Safety Monitoring

1.20.3.1 Data and Safety Monitoring Committee

The Yale Cancer Center Data and Safety Monitoring Committee (DSMC) will provide the primary oversight of data and safety monitoring. The Yale DSMC will review and monitor compliance, toxicity and deviations from this study. The committee is composed of clinical specialists with experience in oncology and who have no direct relationship with the study. Information that raises any questions about participant safety will be addressed with the Principal Investigator.

The DSMC will review this protocol bi-annually, at a minimum. Information to be provided to the committee includes: a study narrative by the PI, a summary DSMC report produced by OnCore (which includes participant accrual, response, trial status history, SAEs, Adverse Events, Deviations and survival); audit results, and monitoring reports as applicable. Other information (e.g. scans, laboratory values) will be provided upon request.

1.20.3.2 Independent safety review committee (SRC)

An independent safety review committee (SRC) assembled by the PI and comprised of one Investigator from both Yale, and Vanderbilt, two external AML experts and a statistician will meet, when required by the sponsor of the trial, and at least once after the inclusion of the first 6 patients, to analyze tolerance and adverse events and decide on any action to be taken.

1.20.4 Audit Plan

The YCCI Office of Quality Assurance and Training will audit the trial at least annually or as determined by the DSMC. The overall principal investigator, project manager and/or monitor may request access to all source documents and other study documentation for on-site or remote monitoring, audit or inspection.

Involvement in this study as a participating investigator implies acceptance of potential audits or inspections, including source data verification, by representatives designated by the Principal Investigator or Yale. The purpose of these audits or inspections is to examine study-related activities and documents to determine whether these activities were conducted, and data were recorded, analyzed, and accurately reported in accordance with the protocol, institutional policy, and any applicable regulatory requirements.

1.20.5 Protocol Research Team Meetings

Scheduled meetings will be held via teleconference monthly, or more frequently depending on the activity of the protocol. These meetings will include the protocol investigators and research staff involved with the conduct of the protocol.

During these meetings the investigators will discuss:

- Safety of protocol participants (adverse events and reporting)
- Validity and integrity of the data (data completeness on case report forms and complete source documentation)
- Enrolment rate relative to expectation of target accrual, (eligible and ineligible participants)
- Retention of participants, adherence to the protocol and protocol violations
- Protocol amendments

1.22 Publication

All of the information arising from this trial shall be considered confidential, at least until completion of the appropriate analysis and subsequent checks by the trial sponsor, coordinating investigator, and statistician.

Any publications, abstracts or presentations that include results from the trial must be submitted to the sponsor for approval.

Any communications, articles, or presentations must also include a section mentioning the Yale University and the organizations that supported the research financially.

The trial's coordinating investigator will be the main (first or last) author.

The first or last author (depending on the position given to the coordinating investigator) will be jointly selected by the sponsor and the CI.

The investigators will be cited in order of the number of patients recruited for multicenter trials or based on their involvement in the protocol and/or the disease. The trial statistician will also be cited.

Similarly, publications of ancillary results (biological studies) shall include the name of the person who carried out the ancillary study, as well as the names of anyone else involved in the ancillary study.

1.23 Ethical and regulatory aspects

The clinical trial must be conducted in accordance with:

- the ethical principles of the current version of the Declaration of Helsinki,
- the guideline for Good Clinical Practice of the International Conference on Harmonization (ICH-E6, 07/17/96),

1.23.1 Institutional Review Board (IRB)

Before conducting biomedical research on human subjects, sites are responsible for submission to their IRB per local policy, including amendments and renewals.

